- Proportion of responders at the 12-month visit based on daily "OFF" time recorded in home "ON/OFF" diaries. A responder is defined as a subject that experiences ≥50% reduction in "OFF" time from Baseline.
- Change in daily "ON" time with troublesome dyskinesia in a subset of subjects who had more than 1 hour of troublesome dyskinesia at Baseline, based on home "ON/OFF" diaries from Baseline to the 12-month visit.
- Change in PDQ-39 scores from Baseline to the 12-month visit.
- Change in EQ-5D-5L scores from Baseline to the 12-month visit.
- Change in UPDRS Part II (ADL) from Baseline to the 12-month visit.
- Change in CGI-Severity and CGI-Improvement from Baseline to the 12-month visit.
- Change in SGI-Improvement from Baseline to the 12-month visit.
- Change in PDSS total score from Baseline to the 12-month visit.
- Change in UPDRS Part III (motor score) from Baseline to the 12-month visit.
- Change from baseline to month 12 in percentage of "OFF" time and percentage of 'Good' ON during the first 3 hours since the subject is awake after 06:00 (6 am)
- Change from baseline to month 12 in ND0612 total dose
- Proportion of patients who reduced ND0612 total dose at any time during the study

Efficacy assessment:

Efficacy will be assessed based on daily "ON" time without troublesome dyskinesia and "OFF" time during waking hours as determined from "ON/OFF" home diary entries. Efficacy will be further explored using PDQ-39 (QoL), EQ-5D-5L (QoL), rating of PD (UPDRS), CGI for severity and improvement, and sleep assessment (PDSS).

Assessment of issues/problems in the infusion pump system:

Number of issues/problems in the pump system and number of subjects with at least one event/problem will be determined for the 12-month treatment period.

User experience assessment:

The user experience with the infusion pump, service, and support will be assessed by an optional questionnaire.

Statistical Analysis:

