11.1.4.3.1 Definition of Efficacy Endpoints

The exploratory efficacy endpoints assessed for 12 months of treatment are:

- Change in daily "ON" time without troublesome dyskinesia (defined as the sum of "ON" time without dyskinesia and "ON" time with non-troublesome dyskinesia) from Baseline to the 12-month visit based on home "ON/OFF" diaries.
- Change in daily "OFF" time from Baseline to the 12-month visit, based on home "ON/OFF" diaries.
- Change in total daily dose of oral LD/DDI from Baseline to the 12-month visit.
- Proportion of responders at the 12-month visit based on daily "OFF" time recorded in home "ON/OFF" diaries. A responder is defined as a subject that experiences ≥50% reduction in "OFF" time from Baseline.
- Change in daily "ON" time with troublesome dyskinesia in a subset of subjects who had more than 1 hour of troublesome dyskinesia at Baseline, based on home "ON/OFF" diaries from Baseline to the 12-month visit.

- Change in PDQ-39 scores from Baseline to the 12-month visit.
- Change in EQ-5D-5L scores from Baseline to the 12-month visit.
- Change in UPDRS Part II (ADL) from Baseline to the 12-month visit.
- Change in CGI-Severity and CGI-Improvement from Baseline to the 12-month visit.
- Change in SGI-Improvement from Baseline to the 12-month visit.
- Change in PDSS total score from Baseline to the 12-month visit
- Change in UPDRS Part III (motor score) from Baseline to the 12-month visit.
- Change from baseline to month 12 in percentage of "OFF" time and percentage of 'Good' ON during the first 3 hours since the subject is awake after 06:00 (6 am)
- Change from baseline to month 12 in ND0612 total dose
- Proportion of patients who reduced ND0612 total dose at any time during the study

The first efficacy endpoint of the change from Baseline to Month 12 in daily "ON" time without troublesome dyskinesia will be based on subject diary data. This will be a within group analysis for each treatment regimen. Subjects will provide data on daily "ON" and "OFF" time for the 2 days prior to the following visits: Baseline (Cohort 2 only), Months 1, 3, 6, 9, and 12 and the Early termination visit (if applicable) and additionally at Months 18, 24, 30, and 36 of the extension period. Subjects in Cohort 1, will be excluded from this analysis.

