1. PREFACE

This Statistical Analysis Plan (SAP) describes the planned analysis and reporting for NeuroDerm clinical trial ND0612H-012 (A multicenter, international, open-label, safety study of ND0612, a solution of levodopa/carbidopa delivered via a pump system as a continuous subcutaneous infusion in subjects with advanced Parkinson's Disease (BeyoND)), and was written in accordance with SOP 002 - Statistical Analysis Plan (NStat – [REDACTED] Procedure). The structure and content of this SAP provides sufficient details to meet the requirements identified by the FDA and International Conference on Harmonization of Technical Requirements for Registration of Pharmaceuticals for Human Use (ICH): E9 Guidance on Statistical Principles in Clinical Trials. All work planned and reported for this SAP will follow internationally accepted guidelines, published by the American Statistical Association, and the Royal Statistical Society, for statistical practice.

The following documents were reviewed in preparation of this SAP:

- Clinical Study Protocol ND0612H-012 Version 9.0 (global Amendment 8): issued on, July 11th 2019
- Case report form (CRF) for ND0612H-012
- ICH E9 Guidance on Statistical Principles for Clinical Trials.
- ICH E3 Structure and Content of Clinical Study Reports (CSRs)

This SAP describes the statistical analyses as it is foreseen before final database lock. The SAP will serve as a complement to the study protocol and supersedes it in case of differences between the SAP and the statistical sections of the protocol. In case of major differences, e.g. changes in the analysis related to the primary endpoint, a protocol amendment will be considered. The SAP may be updated during the study conduct and will be finalized before final database lock.

Based on FDA correspondences dated 27th of March 2019, Neuroderm was advised to focus its safety analysis on AE of Special Interest (AESI), specifically for Infusion Site Skin Reactions (ISR's). In addition, all cases of hypersensitivity reactions (e.g., diffuse skin rash, anaphylaxis and angioedema) should be considered AESI. Cases of Polyneuropathy were also considered as AESI.

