2.3. Exploratory Objectives

Exploratory efficacy objectives will be to assess the following:

- To assess the efficacy of continuous SC infusion of 2 dosing regimens of ND0612 on daily ON time without troublesome dyskinesia (“GOOD ON”) defined as the sum of "ON" time without dyskinesia and “ON” time with non-troublesome dyskinesia, based on home “ON/OFF“ diaries
- To assess the efficacy of continuous SC infusion of 2 dosing regimens of ND0612 on daily “OFF” time based on patient completed home “ON/OFF” diaries
- To assess the efficacy of continuous SC infusion of 2 dosing regimens of ND0612 on daily “ON“ time without any dyskinesia based on home “ON/OFF“ diaries
- To assess the effect of ND0612 on morning “OFF” time using subject-completed “ON/OFF” diary assessments of motor function.
- To assess the effect of continuous SC infusion of 2 dosing regimens of ND0612 on the motor and Activities of Daily Living (ADL) sub-scores of the Unified Parkinson’s Disease Rating Scale (UPDRS)
- To assess the effect of continuous SC infusion of 2 dosing regimens of ND0612 on the

ND0612H-012

Final 4.0

proportion of subjects with an improvement of $\geq 50\%$ in “OFF“ time based on home “ON/OFF“ diaries

- To assess the effect of continuous SC infusion of 2 dosing regimens of ND0612 on “ON” time with troublesome dyskinesia (based on “ON/OFF” home diaries) in a subset of subjects who had more than 1 hour of troublesome dyskinesia at baseline.
- To assess the Clinical Global Impression (CGI: improvement and severity score assessed by investigator), Subject Global Impression (SGI-I: improvement score assessed by subject), Parkinson’s Disease Sleep Scale (PDSS), the 39-Item PD Quality of Life [QoL] Questionnaire (PDQ-39) and the EQ-5D-5L QoL questionnaire.

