- 3.2.3.4.** Change from baseline to month 12 in percentage of “OFF” time during the first 3 hours since the subject is awake after 06:00 (6 am), based on subject’s “ON/OFF” diary assessments on the 3 consecutive days before the visit.
- Subject will be declared as ‘awake’ if found not ‘asleep’ for at least 2 hours after 06:00 (6 am)
 - This endpoint will be derived similarly as the daily “ON time without troublesome dyskinesia in 3.2.3.1. However, only data recorded after 06:00 (6 am) will be used for derivation. At least 5 out of 6 half-hour periods (3 hours) are required to be completed, in order to classify a diary day as valid.
- 3.2.3.5.** Change in total ND0612 total dose from baseline to month 12
- 3.2.3.6.** Proportions of patients who reduced their total ND0612 total dose during 12 month of treatment
- 3.2.3.7.** Proportion of responders at the 12-month visit based on daily “OFF” time recorded in "ON/OFF" diaries. A responder is defined as a subject that experiences $\geq 50\%$ reduction in “OFF” time from Baseline.
- The daily “OFF” time will be calculated as defined in 3.2.3.2. The percentage reduction will be calculated as $(OFF_{\text{Month 12}} - OFF_{\text{baseline}}) / OFF_{\text{baseline}} * 100$. The subjects will be dichotomized as having a percentage reduction of $\geq 50\%$ versus a reduction of $< 50\%$. The patients with missing “OFF” time will be imputed with last available ‘OFF’ time value. .
- 3.2.3.8.** Change in daily “ON” time with troublesome dyskinesia in a subset of subjects who had more than 1 hour of troublesome dyskinesia at Baseline based on home "ON/OFF" diaries from Baseline to the 12-month visit.
- The daily “ON” time with troublesome dyskinesia will be derived similarly as the daily “ON time without troublesome dyskinesia in 3.2.3.1.
- 3.2.3.9.** Change in PDQ-39 summary index and the 8 dimension scores from Baseline to the 12 month visit
- The PDQ-39 questionnaire provides scores on eight dimensions as outlined below:

- mobility (10 items, #1 to 10)
- activities of daily living (6 items, #11 to 16)
- emotional well-being (6 items, #17 to 22)
- stigma (4 items, #23 to 26)
- social support (3 items, #27 to 29)
- cognitions (4 items, #30 to 33)
- communication (3 items, #34 to 36)
- bodily discomfort (3 items, #37 to 39).

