8.2.7. Change in EQ-5D-5L scores from Baseline to the 12-month visit

The health state dimensions will be evaluated by presenting the distribution of responses separately for each of the 5 dimensions at each visit. In addition, the categorical changes (improved, same, and worsened) will be summarized for each of the 5 dimensions at each visit. The VAS score and the health state index score will be analyzed similarly as the “GOOD ON” time replacing baseline “GOOD ON” time with baseline VAS or health state index score as covariate

8.2.8. Change in UPDRS Part II (ADL) from Baseline to the 12-month visit.

The UPDRS Part II (ADL) score change from baseline will be analyzed similarly as the “GOOD ON” time replacing baseline “GOOD ON” time with baseline UPDRS Part II as covariate.

8.2.9. Change in CGI-Severity (CGI-S) and CGI-Improvement (CGI-I) from Baseline to the 12-month visit

The distribution of categorized data (Improvement, non-improvement) will be summarized for each visit using frequencies and percentages. In addition, the distribution of the original uncategorized values will be summarized with frequencies and percentages.

8.2.10. Change in SGI-Improvement from Baseline to the 12-month visit.

The SGI-I will be analyzed similarly as the CGI-I.

8.2.11. Change in PDSS total score from Baseline to the 12-month visit.

The PDSS total score will be analyzed similarly as the “GOOD ON” time replacing baseline “GOOD ON” time with baseline PDSS as covariate.

8.2.12. Change in UPDRS Part III (motor score) from Baseline to the 12-month visit.

The UPDRS Part III (Motor) score will be analyzed similarly as “GOOD ON” time replacing baseline “GOOD ON” time with baseline UPDRS Part III score as covariate.

8.2.13. Morning Akinesia: Change from baseline to month-12 in percentage of “OFF” time during the first 3 hours since the subject is awake after 06:00 (6 am)

The change from baseline to month 12 in percentage of “OFF” time during the first 3 hours since the subject is awake after 06:00 (6 am) will be analyzed similar to the “GOOD ON” endpoint replacing baseline “GOOD ON” time with percentage of OFF during the first 3 hours since the subject is awake at baseline.

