10. CHANGE FROM ANALYSIS PLANNED IN PROTOCOL

- The version of SAP (3.0) was based on Clinical Study Protocol ND0612H-012 Version 8.0 (global Amendment 7): issued on 12 March 2019. At the time when the SAP version 3.0 was finalized, the sponsor endorsed FDA recommendation of a change in the safety primary analyses which were not yet reflected in the protocol. This change was intended to be introduced in a later protocol amendment
- The version of SAP (4.0) was based on Clinical Study Protocol ND0612H-012 Version 9.0 (global Amendment 8): issued on 11 July 2019. There are no changes from this current SAP version (4.0) to the amended protocol (V9.0).

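### The protocol's exploratory morning endpoint has two parts, % OFF and % Good ON, but the SAP defines and analyses only % OFF, so the morning result cannot show which ON state replaced OFF time.

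*Protocol*

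**What the plan says.** **Protocol V10.0.** Section 11.1.4.3.1 pairs the change in percentage of OFF time with the change in "percentage of 'Good' ON during the first 3 hours since the subject is awake after 06:00". The synopsis has the same pairing: "and percentage of 'Good' ON during the first 3 hours since the subject is awake after 06:00 (6 am".

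**SAP 4.0.** The morning period appears in three places, each limited to OFF:
- Objective (2.3): "To assess the effect of ND0612 on morning “OFF” time using subject-completed" diary data.
- Endpoint definition (3.2.3.4): "Change from baseline to month 12 in percentage of “OFF” time during the first 3 hours since the subject is awake".
- Analysis (8.2.13, Morning Akinesia): the Good ON model is reused, but its baseline covariate is replaced "with percentage of OFF during the first 3 hours since the subject is awake at baseline".

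No SAP section defines or models morning Good ON.

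**Precedence and versions.** The SAP Preface says the SAP complements the protocol and "supersedes it in case of differences between the SAP and the statistical sections of the protocol". The protocol (11.1.4.3.2) leaves the definition of endpoints to the SAP, and its section 11.1 asks that departures from the planned analyses be documented there. SAP section 10 states: "There are no changes from this current SAP version (4.0) to the amended protocol (V9.0". The protocol under review is V10.0.

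**The concern.** The diary has four waking states: OFF, ON without dyskinesia, ON with non-troublesome dyskinesia and ON with troublesome dyskinesia. Good ON combines the middle two. A fall in OFF therefore has two possible destinations, Good ON or troublesome ON, and % OFF alone does not say which. The part of the protocol's endpoint that separates them is the part the SAP leaves out.

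A programmer working from the SAP would produce only the OFF part. A listed endpoint component would be missing from the report with no recorded reason, and both the within-regimen change and the Regimen 1 versus Regimen 3 contrast for the morning would be open to two readings. The window is relevant to this population, because Cohort 2 eligibility requires predictable early morning OFF periods (protocol 8.3.2, criteria 7 and 8).

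**Working it through.** The documents give no figure on this point, so there is nothing to reproduce. The check sets the texts side by side and then applies simple arithmetic to the SAP's own window.

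**Step 1. Coverage.**

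| Place | Morning % OFF | Morning % Good ON |
|---|---|---|
| Protocol synopsis | yes | yes |
| Protocol 11.1.4.3.1 | yes | yes |
| SAP 2.3 | yes | no |
| SAP 3.2.3.4 | yes | no |
| SAP 8.2.13 | yes | no |

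SAP 3.2.3.4 says its variable is derived in the same way as Good ON time. That borrows a method; the variable derived is still % OFF.

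**Step 2. What % OFF can distinguish.** Inputs from the documents: six half-hour periods, at least five completed (SAP 3.2.3.4), and the diary states (protocol 10.2.1.1). The diary counts are assumed for illustration: all six periods completed and awake, with a baseline of 4 OFF, 2 Good ON and 0 troublesome ON.

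Formula: change in % = 100 × (periods after - periods at baseline) / 6.

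| One hour (2 periods) moves from OFF to | OFF / Good ON / troublesome after | Change in % OFF | Change in % Good ON |
|---|---|---|---|
| Good ON | 2 / 4 / 0 | 100 × (2 - 4)/6 = -33.3 | 100 × (4 - 2)/6 = +33.3 |
| half each | 2 / 3 / 1 | -33.3 | 100 × (3 - 2)/6 = +16.7 |
| Troublesome ON | 2 / 2 / 2 | -33.3 | 100 × (2 - 2)/6 = 0 |

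The OFF result is the same in all three rows. Over a range of one to four half-hours moved from OFF to troublesome ON, morning % OFF falls by 100 × 1/6 = 16.7 to 100 × 4/6 = 66.7 points, while % Good ON does not change.

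**Step 3. What the second part adds.** Within the window, % OFF + % Good ON + % troublesome ON = 100 of the valid waking entries. So for each subject the change in troublesome ON is minus the sum of the other two changes. In the last row: -(-33.3 + 0) = +33.3. Once both protocol parts are available, the third state follows.

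**Step 4. Whether other outputs fill the gap.**
- Whole-day Good ON and OFF (SAP 8.2.1, 8.2.2) are normalised to 16 waking hours. On a 16-hour waking day with nothing else changed, the last row gives OFF -1.0 h and Good ON 0 h. That is informative, but one hour is 1/16 = 6.25% of the day against 2/6 = 33.3% of the window, and it cannot be assigned to the morning.
- Whole-day ON without any dyskinesia (SAP 8.2.3) has the same limit.
- Whole-day troublesome ON (SAP 8.2.5) is restricted to subjects with more than 1 hour at baseline, so it omits those with little or none.
- Dyskinesia as a TEAE (SAP 7.3.4) is shown by time to first onset, not by time of day.

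**Step 5. A conflict in the same definition.** SAP 3.2.3.4 refers to three consecutive diary days before the visit. Protocol 10.2.1.1 collects two, and the derivation it points to (SAP 3.2.3.1) uses at most the last two.

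**The case against.** The strongest case on the other side has four parts.

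1. **The report as a whole would not hide a shift to troublesome dyskinesia.** The same diaries feed the whole-day models, and dyskinesia gets Kaplan-Meier plots even if it is not among the ten most common TEAEs. This stands. A reader might infer that such a shift would be reported as pure benefit; the documents do not support that, since whole-day OFF would fall with Good ON flat. What remains is narrower: none of these outputs isolates the morning.

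2. **The SAP's silence need not be a deletion.** It calls itself a complement to the protocol, and protocol 11.1.4.3.2 gives a general MMRM or descriptive default for further endpoints. This partly stands. But the same protocol section leaves endpoint definitions to the SAP, and a SAP that defines the morning endpoint in three places as OFF only gives no basis for programming the other part.

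3. **The versions differ.** A reader might infer that the SAP's statement of no changes is false. That cannot be shown: it refers to V9.0, whose endpoint list is not in the documents under review. Either the omission was not recorded or the SAP was not brought up to V10.0. The two documents differ in both cases.

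4. **OFF is the direct measure of morning akinesia, and the reason given for Good ON is the reviewer's.** It is true that neither document explains why Good ON was included, and the protocol's efficacy objectives contain no morning objective. But the protocol does list the component, and the ambiguity of % OFF follows from the diary states themselves.

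A reader might also infer that the gap matters most for Regimen 3, where infusion and an oral dose start on waking. The documents do not establish this: the window counts only time after 06:00, so for a subject who wakes earlier that start may precede it.

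**Conclusion.** The mismatch is real and can be seen directly in the two documents. Following SAP 4.0, one of the two listed components of the morning endpoint is not produced, and the remaining component gives the same score to a shift into Good ON and a shift into troublesome ON (-33.3 points per hour moved, with six valid waking periods).

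The consequence is small. This is one component of one of the 15 exploratory endpoints in protocol 11.1.4.3.1, with no confirmatory testing. It affects reporting and interpretation of the morning window; error rates and the primary safety analysis are untouched. The diary counts are assumed, and nothing in the documents indicates how much morning OFF time, if any, would become troublesome ON.

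**What to change.** - In SAP 3.2.3.4, add the change from baseline to Month 12 in the percentage of ON time without troublesome dyskinesia in the same window, with the same requirement of 5 of 6 completed half-hours. Extend the objective in 2.3 to match.
- In SAP 8.2.13, add the same MMRM for this variable, with its own morning baseline as covariate.
- In SAP 3.2.3.4, reconcile the three consecutive days with the two-day diary collection and derivation, so that the new variable does not inherit the conflict.
- Update the SAP's protocol reference to V10.0. If the sponsor prefers to leave morning Good ON out, record that and the reason in SAP section 10.

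The cost is one more derived variable and one more run of an existing model, on diary data already collected.

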11.1.4.3.2 Methods of Analysis

All efficacy summaries and analyses will be produced for the mITT Set.

For the efficacy endpoints, continuous data will be summarized at each protocol scheduled time point, by treatment regimen, using summary statistics. Actual values and changes from Baseline will be presented. All categorical endpoints will be summarized at each protocol scheduled time point, by randomized treatment regimen, using frequency tabulations.

As the primary purpose of this study is to explore the 2 treatment regimens with regards to efficacy and safety and not to perform confirmatory analyses comparing the treatment

regimens, there will be no formal hypothesis testing performed and adjustments for multiplicity are not required.

The change from Baseline to Month 12 and to the other visits within each treatment regimen in daily "ON" time without troublesome dyskinesia will be estimated using a Mixed Model for Repeated Measures (MMRM) including response data from all scheduled post-baseline visits with no imputation for missing data. The changes from Baseline within each treatment regimen and the comparison between the Regimens will be estimated, separately for each scheduled study visit, from the same MMRM using contrasts. The treatment regimen (Regimen 1 or Regimen 3, when applicable), visit and the interaction between treatment regimen and visit (if applicable) will be included as fixed factors in the MMRM together with the baseline value as covariate. The analysis for the "ON/OFF" home diary, will be performed only for cohort 2. Changes from baseline will be summarized also the overall data. There will be no random effects. An unstructured covariance structure will be assumed, and the denominator degrees of freedom will be computed using the Kenward-Roger method.

The changes in "ON" time without troublesome dyskinesia will be estimated both as hours (normalized to 16 hours of awake time) and as a proportion out of awake time.

In general, all further efficacy endpoints will be summarized and analyzed using either a MMRM analysis, as described above, for continuous endpoints or descriptive statistics for categorical endpoints. Sensitivity analyses of efficacy data will be conducted by excluding the subjects who were randomized to receive Regimen 2. The definition of the endpoints and the statistical analyses will be detailed in the SAP.

Data collected in the extension period will be analyzed similarly as for the 12-month period.

